3.2.1 Inclusion Criteria

Patients who meet all the following inclusion criteria will be included in the study:

- Documented diagnosis of neurological disorder or NMD
- Age 5-80 years
- one or more respiratory exacerbations in the past 6 months or two or more respiratory exacerbations in the past 12 months, which require unplanned or unscheduled medical intervention.
- Ability to perform OLE therapy as directed
- Signed informed consent (and assent if minor subject)

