3.3.3.1 Baseline Study Visit: During the baseline visit, study staff will review the informed consent form (and assent form if minor subject) with the study subject and/or caregiver(s). If the patient/caregiver agrees to participate in the study, the informed consent form (and assent form, if applicable) will be signed. A pregnancy test will be administered to female subjects of childbearing age. Inclusion and exclusion criteria will then be assessed and documented and (if eligible) the subject will be enrolled in the study. The study schedule and subject responsibilities will then be reviewed with the subject/caregiver. During the Baseline Visit, the subject's current respiratory therapy regimen and required respiratory support will be documented. A quality of life (QOL) assessment using the Severe Respiratory Insufficiency (SRI) questionnaire will be completed for each subject to assess QOL rating during the pre-treatment period and a Satisfaction Survey questionnaire will be completed by the subject and/or caregiver as an assessment of the current therapy regimen.

3.3.3.2 Documentation of Demographics, Medical History and Pulmonary Exacerbations: Demographic data will be collected for patients enrolled in the study. Medical records for each enrolled subject will be obtained and reviewed to obtain relevant patient medical history and to document pulmonary comorbidities and history at the time of enrollment. Current respiratory related medications and treatments will be documented. Pulmonary exacerbations (as defined in the study endpoints) that occurred in the 12-month period prior to enrollment in the study will be documented. Subsequent medical records will be obtained during the active treatment period and will be used to determine and to document the occurrence of pulmonary exacerbations during that period.

- **Demographic Data**

The following demographic data will be collected: Age, Height, Weight, Race, Ethnicity and Gender.

PROTOCOL TITLE

Evaluation of Oscillation and Lung Expansion (OLE) using The Volara® System for treatment of respiratory complications in patients with neuromuscular disease in the home setting

Final Protocol

Protocol Number: CR-RR-2020-005

Date: 11May2022

- **Pulmonary Related Medical History**

History of asthma, cystic fibrosis, bronchiectasis, COPD, obstructive sleep apnea, documented obesity (BMI $\geq 30 \text{ kg m}^2$), other pulmonary condition(s) will be documented.

- **Medications**

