Respiratory related medications such as bronchodilators, or mucolytics that are prescribed for each study subject during the 12-month pre-treatment period, as well as respiratory medications that are prescribed during the active treatment period will be documented.

- **Respiratory Status**

Respiratory status including required respiratory support (e.g., invasive mechanical ventilation, noninvasive ventilation, requirement for tracheostomy, O₂ level, etc.) will be documented from the patient medical record for each subject.

- **Respiratory Treatments**

Respiratory treatments, including mechanical insufflation/exsufflation or other lung expansion or airway clearance therapy, or other therapies to improve respiratory status will be documented from the patient medical record.

- **Pulmonary Exacerbations**

Pulmonary exacerbations (as defined in the study endpoints) which occurred during the 12-month pre-treatment period or during the active treatment period will be documented.

3.3.3.3 Pulmonary Function Testing: Pulmonary function testing will be completed virtually by an external research organization which specializes in home pulmonary function testing (Zephyrx). This testing will be scheduled separately following enrollment into the study. Baseline parameters will be assessed, including slow vital capacity (SVC), Peak Cough Flow (PCF), Resting SpO₂, and Maximal Inspiratory Pressure (MIP). With this study population, certain subjects may not be able to complete a valid test for all pulmonary function procedures. If unable to complete, a procedure, the inability to complete that procedure will be documented.

PROTOCOL TITLE

Evaluation of Oscillation and Lung Expansion (OLE) using The Volara® System for treatment of respiratory complications in patients with neuromuscular disease in the home setting

Final Protocol

Protocol Number: CR-RR-2020-005

Date: 11May2022

3.3.3.4 Run-in Period: Following the Baseline Study Visit, a run-in period of two to four weeks will be completed by the subject prior to initiation of OLE therapy. During this period, the subject/caregiver will document use of MIE and other current airway clearance and lung expansion therapy/maneuvers for each day in the run-in period.

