3.3.6 Study Flow and Timeline

The study flow and timeline of events and data collection periods is shown below in and Figure 1.

FIGURE 1

PROTOCOL TITLE**Evaluation of Oscillation and Lung Expansion (OLE) using The Volara® System for treatment of respiratory complications in patients with neuromuscular disease in the home setting**

Final Protocol

Protocol Number: CR-RR-2020-005**Date:** 11May2022**3.5 Statistical Methods and Analysis****3.5.1 Sample Size Estimation**

The sample size for this study is a convenience sample. Resulting data on the outcomes associated with the OLE may provide preliminary data on effectiveness of therapy and help to provide definition of the effect size and variability and the number of subjects required for subsequent studies.

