4. ICU LOS
5. Number of Outpatient Visits
6. Antibiotic Use Days
7. Pulmonary Function Testing
 - SVC
 - PCF
 - Resting SpO₂
 - MIP
8. QOL Assessment
9. Adherence to OLE Therapy Regimen
10. Patient/Caregiver Satisfaction

Comparison of Pre-treatment and Active Treatment Periods

Rate of exacerbation and health care utilization will be evaluated to compare the active treatment period and the control periods (six-month period immediately prior to active treatment and six-month seasonally equivalent time-period). Remaining endpoints will compare baseline assessments to assessments obtained during the active treatment period. Comparisons will be conducted for the purpose of identifying any statistical associations that can be attributed to use of OLE treatment with The Volara® System.

General Study Information**4.1 Technical Support for Device(s)**

Technical support will be performed by Hillrom following routine service practices (contact details will be provided).

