### **1.2.2 Determination of Sample Size**

A total of approximately 70 subjects will be enrolled. The sample size for this study is a convenience sample. This is a descriptive study with no formal hypothesis testing.

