#### 2.4.1.1 Derivation of Primary Endpoint

Exacerbations of pulmonary disease are defined as changes in respiratory status requiring intervention. Documentation of pneumonia or respiratory infection, change in chest x-ray, changes in requirement for respiratory support necessitating any of the interventions below will be considered an exacerbation of pulmonary disease:

- Hospitalization
- ED Visit
- Unscheduled Antibiotics for Respiratory Infection
- Unscheduled outpatient visit

Pulmonary exacerbation events that occurred during the 12-month pre-treatment period and the active treatment period will be recorded in the data. Pulmonary exacerbation events that occurred prior to the Volara® start date occurred in the pre-treatment period. Pulmonary exacerbation events that occurred on or after the Volara® start date occurred in the active treatment period. The paired difference in pulmonary exacerbation events for each subject will be calculated as follows:

$$\begin{aligned} & \text{Number of pulmonary exacerbations in active treatment period} \\ & - \text{Number of pulmonary exacerbations in 6 months prior to treatment start} \end{aligned}$$

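### The primary contrast uses as its control the months on which patients were selected, and the protocol's seasonally equivalent control is missing from the SAP and not listed as a change

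*SAP*

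**What the plan says.** - **Entry.** Protocol 3.2.1 requires "one or more respiratory exacerbations in the past 6 months or two or more respiratory exacerbations in the past 12 months". At the baseline visit (3.3.3.1), "Inclusion and exclusion criteria will then be assessed and documented".
- **Gap before treatment.** Under Protocol 3.3.3.4, "a run-in period of two to four weeks will be completed by the subject prior to initiation of OLE therapy".
- **Primary contrast.** SAP 2.4.1.1 subtracts the "Number of pulmonary exacerbations in 6 months prior to treatment start" from the active-period count. SAP 2.4.1.2 summarizes that paired difference with a two-sided 95% interval. The per-protocol analysis repeats it in a subset. Events from the earlier half of the 12-month look-back are only listed.
- **Control periods in the protocol.** Protocol 3.5.2 names two for exacerbations and health care utilization: "six-month period immediately prior to active treatment and six-month seasonally equivalent time-period". The stated purpose is "identifying any statistical associations that can be attributed to use of OLE treatment".
- **Control periods in the SAP.** SAP 2.1.2 defines no seasonal period, and the utilization endpoints in 2.4.2.2 to 2.4.2.7 are summarized for the prior six months only. SAP section 3 lists one change, that adherence will not be analyzed.
- **Status of the study.** SAP 1.2.2: "This is a descriptive study with no formal hypothesis testing". Protocol 3.5.1 says the data "may provide preliminary data on effectiveness of therapy and help to provide definition of the effect size and variability".

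**The concern.** A patient group chosen for recent events will, on average, have fewer events afterwards even if nothing changes. Here the window used for choosing and the window used as control almost coincide, so part of any fall from control to active period would be regression to the mean. Neither document, as supplied, says so. The reported mean difference and interval would then mix a device effect with a selection effect, and that mixture could be taken as the effect size for planning later studies.

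The second issue is separate. Respiratory events may vary by season, and the immediately prior six months cover the opposite half of the calendar year from the treatment period. The protocol's second control was the only one matched on calendar months.

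**Working it through.** **Overlap.** Selection looks back from baseline and the control looks back from Volara start. With a run-in of 2 to 4 weeks, the shared part of the 26-week control is 26 - 4 = 22 to 26 - 2 = 24 weeks.

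**No figure to reproduce.** The sample of about 70 is a convenience sample, and no event rate, SD or effect size is given. The rates below are assumptions: mean events per six months in the source population before selection.

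**Hand check, same rate m for everyone, run-in r = 3 weeks, no device effect.** A patient fails to qualify only with no event in the latest 26 weeks before baseline and at most one in the 26 weeks before that:

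P(qualify) = 1 - e^(-2m)(1 + m)

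Any event in the shared 26 - r weeks is enough for entry, and the run-in weeks are unselected:

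Expected control count = [m(26 - r)/26] / P + m·r/26; expected active count = m

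- m = 0.5: P = 0.448; control = 0.442/0.448 + 0.058 = 1.04; active 0.50; change -52%.
- m = 1: P = 0.729; control = 0.885/0.729 + 0.115 = 1.33; active 1.00; change -25%.
- m = 3: P = 0.990; control = 2.654/0.990 + 0.346 = 3.03; active 3.00; change -1%.

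**Patients with different rates.** Gamma-Poisson rates with shape 0.5, 1, 2 or infinity (infinity means identical patients), both entry routes, the FAS condition, complete follow-up and run-in events counted:

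| Assumed rate | Spurious change, SAP contrast |
|---|---|
| 0.5 | -26% to -52% |
| 1.0 | -13% to -25% |
| 1.5 | -8% to -11% |
| 2.0 | -5% to -7% |
| 3.0 | -1% to -3% |

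The sign is negative in all 20 scenarios. At rate 1, shape 1, the control mean is 1.76 and the active mean 1.47. The active mean also exceeds the source mean of 1.00, because selection picks patients with higher rates. Only 1.76 - 1.47 = 0.29 of the 0.76 control excess is regression to the mean. A 2-week or 4-week run-in gives -17% or -16%.

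**Effect on the interval.** In a separate simulation with n = 70 and no effect, the 95% interval lay wholly below zero in 54% to 99.6% of studies at rate 0.5, 20% to 54% at rate 1 and 7% to 10% at rate 2, against a nominal 2.5%.

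**The second control.** The active period is months 0 to 6 after start, so the same calendar months a year earlier are months 7 to 12 before start. Entry by two events in 12 months, and the few weeks of the six-month look-back that precede month 6, also select on this window. For identical patients at m = 1:

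Expected count = [0.885(1 - e^(-2)) + 0.115]/0.729 = 1.21

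The spurious difference is -0.21, which is 63% of -0.33. Over the scenarios, the months 7 to 12 contrast in the FAS keeps about 46% of the bias at rate 0.5 and 51% to 88% at rates 1 to 3.

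**Seasonality, illustration only.** With an assumed sinusoidal rate of 30% amplitude and no selection, one subject's ratio of active to prior six months runs from 0.68 to 1.47 depending on start month. The ratio to the seasonally equivalent months stays at 1.00.

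**What can reverse the sign.**
- *Progression* (shape 1, assumed 20% yearly rise, rates 0.5/1/1.5/2/3): SAP contrast -31/-11/-3/+2/+5%; months 7 to 12 contrast in the FAS -5/+7/+12/+15/+17%.
- *Run-in events missed* (shape 1): at rate 1 the control loses 1.47 × 3/26 = 0.17 and falls to 1.59, so the change is -8% instead of -17%. At rates 1.5, 2 and 3 it is about 0, +5% and +9%.

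**The case against.** - **The study is descriptive.** SAP 1.2.1 says frequencies will be displayed where Protocol 3.1.1 says compared, and the SAP disclaims testing. This stands against any reading that a type I error rate is inflated, since no test is planned. It does not answer the point: the main output is an interval for a before-after difference, and the protocol speaks of attribution and effect size.
- **The overlap comes from the protocol.** Protocol 3.5.2 itself plans the prior-six-month comparison. True, and that contrast should stay. But the protocol paired it with a second control.
- **The direction is not assured.** This stands. The population includes progressive diseases. Protocol 3.3.3.2 has exacerbations documented for the 12 months before enrollment, whereas the synopsis and 3.1.1 say before OLE initiation. If chart review stops at enrollment, run-in events depend on patient or caregiver report at one month. A reader might infer that any observed fall must be an artefact, or that the bias always favours the device. The documents support neither.
- **The large figures need low rates.** This stands. The -52% requires 0.5 events per six months and identical patients, which is unlikely across ages 5 to 80 and these diagnoses.
- **The seasonal control addresses season, not selection.** Largely right. A reader might infer that restoring it cures the selection bias; on the figures above, about half or more usually remains.
- **The omission may be declared elsewhere.** The SAP's contents list a revision history that was not in the supplied text. What can be said is that section 3, the place for such changes, does not list it.

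**Conclusion.** The point holds, in two parts.

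First, the SAP's only primary contrast is exposed to regression to the mean from the entry criterion, and the SAP does not say so. Given stable rates, complete follow-up, counted run-in events and no device effect, the direction follows from the design. The size is uncertain: about -52% to -1% over assumed rates of 0.5 to 3 events per six months, large if events are infrequent and small if most patients have several per half-year. Relaxing stability or run-in counting can cancel or reverse it.

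Second, and independent of any simulation, the protocol's seasonally equivalent control is absent from the SAP for exacerbations and utilization, and SAP section 3 does not list that departure.

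No single contrast is best in every case, so the two should be shown together. This should be fixed, but as a matter of interpretation and reporting. It does not show that the therapy has no effect.

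**What to change.** 1. In SAP 2.1.2 and 2.4.1.1 to 2.4.1.2, keep the current contrast. Report beside it, in the FAS and with a 95% interval, active minus the seasonally equivalent period, defined as months 7 to 12 before Volara start. Give the same by-period summary for the utilization endpoints, or list the omission in section 3.
2. Add a qualitative statement: the prior-six-month contrast is subject to regression to the mean from the entry criterion; the months 7 to 12 contrast in all FAS subjects reduces this bias without removing it, and is more exposed to progression because the windows lie a year apart. Put no percentages in the SAP, since they rest on assumed rates.
3. State that run-in events belong to the pre-treatment period, in line with SAP 2.4.1.1, and reconcile Protocol 3.3.3.2 with the synopsis and 3.1.1 so that chart review covers the run-in.
4. Optional: a sensitivity analysis of the months 7 to 12 contrast in subjects with at least one exacerbation between month 6 before start and enrollment. Such an event satisfies the exacerbation criterion and the FAS condition by itself, so months 7 to 12 play no part in that selection. Under stable rates the expected difference is zero. It does not address the other entry criteria, such as the exclusions for continuous ventilation and anticipated respiratory hospitalization. Label it post hoc if data had been seen.

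**Cost.** SAP wording and a little programming; no new data, because 12 months of events are already recorded, and no change to the FAS definition. In the scenarios, the restored contrast has an interval 0% to 11% wider than the current one. The optional subset drops about 6% to 20% of subjects and is about 4% to 14% wider (half-width 0.45 against 0.41 at rate 1, shape 1, n = 70).

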#### 2.4.1.2 Analysis of Primary Endpoint

The primary endpoint of the study, frequency of exacerbations of pulmonary disease requiring medical intervention, will be analyzed descriptively by study period (active treatment and 6-month pre-treatment) using n, mean, standard deviation, minimum, median, and maximum. The paired difference in the frequency of exacerbations of pulmonary disease requiring medical intervention between study periods (active treatment period - 6-month pre-treatment historical control period) will also be analyzed descriptively with n, mean, standard deviation, minimum, median, maximum and 95% two-sided confidence interval (CIs) for the mean paired difference. All pulmonary exacerbation events that occurred in the 12-month pre-treatment period and the active treatment period will be listed.

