## 1. STUDY DETAILS

This statistical analysis plan (SAP) is provided to describe the framework for the reporting, summarization, and statistical analysis methodology of the safety and efficacy parameters measured throughout the study. It is based on clinical trial protocol CR-RR-2020-005 Revision D, dated 11 MAY 2022.

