### 2.1.2 Study Periods

The study periods include the 12-month pre-treatment historical control period, 6-month pre-treatment historical control period, and the active treatment period.

The active treatment period begins once a subject has started therapy with The Volara® System.

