##### **2.4.2.2.2 Analysis of Number of Hospital Admissions**

The number of hospital admissions will be analyzed descriptively by study period (active treatment and 6-month pre-treatment) using n, mean, standard deviation, minimum, median, and maximum. All hospital admissions that occurred in the 12-month pre-treatment period and the active treatment period will be listed.

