#### **2.4.2.5 ICU Length of Stay**

##### **2.4.2.5.1 Derivation of ICU Length of Stay**

Total ICU length of stay will be determined for each study subject by summing the calculated number of days spent in the ICU for each admission, from time of admission to time of discharge. Date of admission and date of discharge will be recorded in the data for each study period. The sum of all ICU days for each subject will be calculated for the pre-treatment period and for the active treatment period. The number of ICU days for each admission will be calculated as follows (standardized to the number of days):

*Date of Discharge – Date of Admission + 1*

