##### **2.4.2.5.2 Analysis of ICU Length of Stay**

Total ICU length of stay will be analyzed descriptively by study period (active treatment and 6-month pre-treatment) using n, mean, standard deviation, minimum, median, and maximum.

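### The SAP drops the protocol's seasonally equivalent control period from every planned comparison, and its Section 3 does not record the change

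*SAP*

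**What the plan says.** The comparison paragraph of Protocol 3.5.2 covers exacerbation rate and health-care utilisation. It sets the active period against two control periods: "six-month period immediately prior to active treatment and six-month seasonally equivalent time-period".

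The SAP names its source: "It is based on clinical trial protocol CR-RR-2020-005 Revision D, dated 11 MAY 2022". That is the date of the protocol under review. The SAP then says:

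- **Section 2.1.2:** "The study periods include the 12-month pre-treatment historical control period, 6-month pre-treatment historical control period, and the active treatment period". No seasonal window is defined.
- **Section 2.4.1.1:** the paired difference subtracts "Number of pulmonary exacerbations in 6 months prior to treatment start".
- **Section 2.4.1.2:** one contrast with a 95% CI, "active treatment period - 6-month pre-treatment historical control period".
- **Analysis paragraphs of 2.4.2.2 to 2.4.2.7** (admissions, hospital days, ICU admissions, ICU days, outpatient visits, antibiotic days): each is summarised "by study period (active treatment and 6-month pre-treatment").
- **Section 3:** one change from the protocol, the removal of the adherence analysis.

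Two derivations are loosely worded. Section 2.4.2.5.1 says "The sum of all ICU days for each subject will be calculated for the pre-treatment period and for the active treatment period", without saying whether the pre-treatment period is six or twelve months, and 2.4.2.7.1 does the same for antibiotic days. Their analysis paragraphs settle on six months; for ICU days, "Total ICU length of stay will be analyzed descriptively by study period (active treatment and 6-month pre-treatment").

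**The concern.** Each patient is his or her own control and there is no parallel arm, so the choice of control window is the only protection against anything that varies with time. The events are chest infections, antibiotic courses, unscheduled visits and admissions, which may well follow the season. For a patient with six full months of treatment, the six months just before the start share no calendar dates with the treated months. The protocol's second window is the only safeguard it names against this.

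If starts cluster in one part of the year, a seasonal swing goes straight into the primary paired difference and its CI, in either direction. Events from all 12 months will be listed, so the missing contrast could be built later, but by then the choice to look at it would be made with the results in view.

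**Working it through.** **1. Text comparison**

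| Item | Protocol 3.5.2 | SAP |
|---|---|---|
| Control periods compared with active treatment | 2 | 1 (2.4.1.2; 2.4.2.2–2.4.2.7) |
| Seasonal window defined | Named, not dated | No (2.1.2) |
| Use of months −12 to −6 before start | Seasonal comparison (by inference) | FAS membership and listings only |
| Recorded as a change | – | No (Section 3 lists adherence only) |

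The plan states no figure that depends on this. About 70 is a convenience sample, so there is nothing to reproduce.

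**2. Size of a seasonal shift, before patient selection.** The documents give neither event rate nor amplitude, so both are assumed. Let the yearly rate be λ, varying as 1 + a·cos(2πt) with t in years, with no device effect. For a start at date s:

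- active six months minus prior six months = −(2/π)·λ·a·sin(2πs)
- active six months minus the same dates one year earlier = 0, because the season repeats

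If starts are uniform over W years centred on the worst date, the first line averages to ±(2/π)·λ·a·sin(πW)/(πW). With λ = 2 and a = 0.3 the leading factor is 0.382. For W = 0.5, 0.382 × 0.637 = 0.24.

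**3. With the plan's own selection rules.** A null simulation added:

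- a 3-week run-in (Protocol 3.3.3.4 allows two to four weeks)
- eligibility at enrolment: at least 1 event in 6 months or at least 2 in 12 (Protocol 3.2.1)
- the FAS rule: at least 1 event in the 12 months before start (SAP 1.3.1)
- Poisson counts and n = 70

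With no season, active minus prior six months averages −0.33 with a 95% CI half-width of 0.33. That fall is regression to the mean, not season. The seasonal displacement is measured from it:

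| Spread of starts | Formula, unselected | Simulated, selected | Null studies with CI wholly below zero |
|---|---|---|---|
| No season | 0 | 0 | 50% |
| 3 months | ±0.34 | ±0.37 | – |
| 6 months | ±0.24 | ±0.26 (means −0.59 or −0.07) | 94% or 6% |
| 9 months | ±0.11 | ±0.13 | 76% or 23% |
| 12 months | 0.00 | 0.00 | 49–50% |
| 18 months | ±0.08 | ±0.09 | 30% or 69% |
| 24 months | 0.00 | 0.00 | – |

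At a 6-month spread, 20% amplitude gives ±0.17 and 50% gives ±0.44. Over 1 to 3 events a year, with or without gamma variation between patients (shape 1), 30% amplitude gives ±0.15 to ±0.51, or 0.6 to 1.0 half-widths.

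**4. The omitted contrast in the same setting.** Against months −12 to −6 the null mean is −0.21 with no season, and about −0.16 or −0.26 at a 6-month spread. Season now moves it by ±0.05, which is left over from selection. CIs lie wholly below zero in about 22%, and in 17% or 30%. At a 6-month spread the CI covers its own no-season value in 94% of studies, against 66–67% for the SAP contrast.

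**5. Side check on selection, no season.** With mean L per six months, and ignoring run-in, P(eligible) = 1 − e^(−2L)(1 + L). The expected count among eligible patients is L/P in the latest six months and L(1 − e^(−2L))/P in the earlier six. For L = 1, P = 0.729 and the two means are 1.371 and 1.186, so the null differences are −0.37 and −0.19. The earlier window is less inflated by the entry rule, but it is not free of it.

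**The case against.** The strongest reply is that this is a descriptive pilot with a convenience sample and no hypothesis test, and that Protocol 3.5.2 leaves the detail of the primary analysis to the SAP. The protocol never dates its seasonal window and does not ask for a paired difference with its own CI. All 12 months of events are listed, so nothing is lost for good. That limits the weight of the point, but not its substance. The protocol's commitment is to compare with both periods, and the SAP makes only one comparison while still giving that one a CI.

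Three further points stand in part:

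- **Size.** Rate, amplitude and calendar are assumed, and starts are centred on the worst date. With even enrolment over 12 or 24 months the seasonal shift vanishes, and in the headline 6-month case it is smaller than the half-width. The 50% of null CIs below zero with no season comes from the entry rule and must not be blamed on season.
- **Record of the change.** The SAP's revision-history page is not available and might mention it. What can be shown is that Section 3, whose purpose is to list departures, does not.
- **Timing.** The SAP is dated 28 May 2024 and Section 2.6.2 describes study conduct in the past tense. If outcomes have already been seen, adding the contrast now brings less of the benefit of pre-specification.

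A rule for early leavers is a separate question that affects the existing contrast as well. It matters here only because both windows should be treated alike.

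**Conclusion.** The concern holds. The SAP plans no contrast and no summary against the seasonally equivalent period that its own protocol version names, for the primary endpoint or for any of the six utilisation endpoints, and Section 3 does not say so. That much rests on the text alone.

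The numerical harm is conditional and its direction unknown. Under the stated assumptions it ranges from nothing, with starts spread evenly over whole years, to about ±0.26 events per patient (roughly 0.8 of a half-width, 0.26/0.33) when starts fall within six months around the worst date. It is larger with narrower enrolment or stronger seasonality. This should be fixed before reporting. It does not make the study uninterpretable.

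**What to change.** 1. In SAP 2.1.2 define the seasonally equivalent control period. The natural reading is the active window shifted back 12 months, that is, months −12 to −6 before the Volara start. Because the protocol gives no dates, say that this is the definition adopted.
2. In SAP 2.4.1 report active minus seasonally equivalent, with the same descriptive statistics and 95% CI, beside the existing contrast and not in its place. Add the period to the summaries in 2.4.2.2 to 2.4.2.7.
3. In 2.4.2.5.1 and 2.4.2.7.1 state which control period is meant.
4. Apply one exposure rule for early leavers to both control windows: both a full six months, or both cut to the observed active time.
5. If the comparison is to stay out, record that with the reason in Section 3. If it is added after outcomes were seen, report that too.

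The cost is SAP wording and extra table columns. Months −12 to −6 are covered by the chart review whether its 12 months end at therapy start (Protocol 3.1.1) or at enrolment (Protocol 3.3.3.2), since the run-in only moves the second version earlier.

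The added window has limits that should be stated. It lies further from treatment and assumes that seasons repeat from year to year. It also keeps some regression to the mean: with no season and no device effect, at 1 to 3 events a year, the false fall is 0.12–0.25 events, against 0.19–0.55 for the prior six months.
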